1.2 Study Objectives

The study objectives are as follows:

Objective(s)	Endpoint(s)
Primary	
To evaluate the efficacy of an experimental dentifrice containing 67% w/w sodium bicarbonate, 0.2% w/w HMW sodium hyaluronate and 0.221% w/w sodium fluoride compared to a fluoride control dentifrice, for the assessment of gingivitis, as measured by a Bleeding Index (BI), after 6 weeks' twice daily toothbrushing.	Number (no.) of bleeding sites at 6 weeks.
Secondary	
To evaluate the efficacy of an experimental dentifrice containing 67% w/w sodium bicarbonate, 0.2% w/w HMW sodium hyaluronate and 0.221% w/w sodium fluoride compared to a 67% w/w sodium bicarbonate/ 0.221% w/w sodium fluoride dentifrice, for the assessment of gingivitis, as measured by a Bleeding Index (BI), after 6 weeks' twice daily toothbrushing.	Number (no.) of bleeding sites at 6 weeks.
To evaluate the efficacy of a dentifrice containing 67% w/w sodium bicarbonate/ 0.221% w/w sodium fluoride compared to a fluoride control dentifrice, for the assessment of gingivitis, as measured by a Bleeding Index (BI), after 6 weeks' twice daily toothbrushing.	Number (no.) of bleeding sites at 6 weeks.
Exploratory	
To evaluate the efficacy of an experimental dentifrice containing 67% w/w sodium bicarbonate, 0.2% w/w HMW sodium hyaluronate and 0.221% w/w sodium fluoride compared to a 67% w/w sodium bicarbonate/ 0.221% w/w sodium fluoride dentifrice, with both compared to a fluoride control dentifrice, for the assessment of gingivitis, as measured by a Bleeding Index (BI), over 2 weeks' twice daily use.	No. of bleeding sites at 3 days, 1 and 2 weeks.
To evaluate the efficacy of an experimental dentifrice containing 67% w/w sodium bicarbonate, 0.2% w/w HMW sodium hyaluronate and 0.221% w/w sodium fluoride compared to a 67% w/w sodium bicarbonate/ 0.221% w/w sodium fluoride dentifrice, with both compared to a fluoride control dentifrice, for the assessment of gingivitis, as	Mean BI at 3 days, 1, 2 and 6 weeks.

GlaxoSmithKline Consumer Healthcare Confidential

SOP-208559 Statistical Reporting and Analysis plan template v2.0

Experimental Dentifrice: 67% w/w sodium bicarbonate, 0.2% w/w high molecular weight sodium hyaluronate and 0.221% w/w sodium fluoride

208175

Final Version 1.0 Statistical Reporting and Analysis Plan Text (Amendment 1),
10 Jun 2021

Objective(s)	Endpoint(s)
measured by a Bleeding Index (BI), over 6 weeks' twice daily use.	
To evaluate the efficacy of an experimental dentifrice containing 67% w/w sodium bicarbonate, 0.2% w/w HMW sodium hyaluronate and 0.221% w/w sodium fluoride compared to a 67% w/w sodium bicarbonate/ 0.221% w/w sodium fluoride dentifrice, with both compared to a fluoride control dentifrice, for the assessment of gingivitis, as measured by Modified Gingival Index (MGI), over 6 weeks twice daily use.	Mean MGI at 3 days, 1, 2 and 6 weeks.
To evaluate the efficacy of an experimental dentifrice containing 67% w/w sodium bicarbonate, 0.2% w/w HMW sodium hyaluronate and 0.221% w/w sodium fluoride compared to a 67% w/w sodium bicarbonate/ 0.221% w/w sodium fluoride dentifrice, with both compared to a fluoride control dentifrice, for the assessment of plaque accumulation, as measured by a Plaque Index (TPI; overall and interproximal), over 6 weeks twice daily use.	Mean TPI (overall and interproximal) at 3 days, 1, 2 and 6 weeks.
To evaluate and compare MGI and mean BI in low (<45 bleeding sites) and high (>45 bleeding sites) BI subgroups following twice daily use of an experimental dentifrice containing 67% w/w sodium bicarbonate, 0.2% w/w HMW sodium hyaluronate and 0.221% w/w sodium fluoride, a 67% w/w sodium bicarbonate/ 0.221% w/w sodium fluoride dentifrice and a fluoride control dentifrice, over 6 weeks twice daily use.	Mean MGI and mean BI at 3 days, 1, 2 and 6 weeks within each subgroup (low and high number of bleeding sites)
Safety	
To assess the oral tolerability of an experimental dentifrice containing 67% w/w sodium bicarbonate, 0.2% w/w HMW sodium hyaluronate and 0.221% w/w sodium fluoride, a 67% w/w sodium bicarbonate/ 0.221% w/w sodium fluoride dentifrice, and a fluoride control dentifrice over 6 weeks twice daily use.	Treatment-emergent adverse events over 6 weeks.

Experimental Dentifrice: 67% w/w sodium bicarbonate, 0.2% w/w high molecular weight sodium hyaluronate and 0.221% w/w sodium fluoride

208175

Final Version 1.0 Statistical Reporting and Analysis Plan Text (Amendment 1),
10 Jun 2021

1.3 Treatments

There are 4 products used in this study – 1 washout product and 3 investigational/study products. The three study product groups in this study are:

- Experimental Dentifrice
- Positive Control Dentifrice
- Negative Control Dentifrice

The following study products will be supplied by the Clinical Supplies Department, GSK CH:

Table 1-2 Investigational/Study Product Supplies

	Washout Product	Experimental Product	Positive control	Negative control
Product Name	Dentifrice containing 1000ppm fluoride as SMFP (Colgate Cavity Protection)	Experimental dentifrice containing 67% w/w sodium bicarbonate, 0.2% w/w sodium hyaluronate and 0.221% w/w sodium fluoride	Dentifrice containing 67% w/w sodium bicarbonate and 0.221% w/w sodium fluoride	Dentifrice containing 1100ppm fluoride as sodium fluoride (Crest Cavity Protection)
Product Master Formulation Code (MFC)	Canadian marketed product (NPN no. CCI [REDACTED])	CCI [REDACTED]	CCI [REDACTED] (NPN no. CCI [REDACTED])	Canadian marketed product (NPN CCI [REDACTED])
Dose/ Application	Full ribbon of toothpaste to cover the head of toothbrush provided			
Route of Administration	Oral topical			
Usage Instructions	Subjects will brush their teeth for one timed minute twice a day (morning and evening)			
Return Requirements	All used/unused samples to be returned			

Experimental Dentifrice: 67% w/w sodium bicarbonate, 0.2% w/w high molecular weight sodium hyaluronate and 0.221% w/w sodium fluoride

208175

Final Version 1.0 Statistical Reporting and Analysis Plan Text (Amendment 1),
10 Jun 2021

1.4 Sample Size Calculation

No formal study powering was conducted. Forty (40) randomized subjects per product group are deemed to be sufficient for generating sufficient efficacy and safety data to evaluate the combination product (sodium bicarbonate and sodium hyaluronate), with sodium bicarbonate dentifrice and regular fluoride dentifrice in this PoP study.

Sufficient subjects will be screened (approximately 160) by the study site so that at least 120 subjects (approximately 40 per product group) who fulfil all the entry criteria will be randomized, which should ensure that approximately 36 evaluable subjects per group complete the week 6 assessment (thus allowing for a 10% drop-out rate).

2 Planned Analyses

2.1 Interim Analysis

No interim analysis is planned.

2.2 Final Analyses

The final planned analyses will be performed after the completion of the following sequential steps:

- All subjects have completed the study as defined in the protocol.
- All required database cleaning activities have been completed and database has been locked.
- All criteria for unblinding the randomization codes have been met and the randomization codes have been distributed.

3 Considerations for data analyses and Data Handling Conventions

3.1 Baseline Definition

For all endpoints, the baseline value will be the latest pre-dose assessment with a non-missing value (Visit 2, Day 0).

Unless otherwise stated, if baseline data is missing no derivation will be performed and will be set to missing.

Experimental Dentifrice: 67% w/w sodium bicarbonate, 0.2% w/w high molecular weight sodium hyaluronate and 0.221% w/w sodium fluoride

208175

Final Version 1.0 Statistical Reporting and Analysis Plan Text (Amendment 1),
10 Jun 2021

3.2 Subgroups/Stratifications

Subjects will be stratified by gender (Male/Female) and baseline number of bleeding sites (NBS) (Low: < 45 bleeding sites; High: \geq 45 bleeding sites).

Based on above stratification factors, there will four strata as follows:

- Stratum 1: Male, Baseline NBS < 45.
- Stratum 2: Male, Baseline NBS \geq 45.
- Stratum 3: Female, Baseline NBS < 45.
- Stratum 4: Female, Baseline NBS \geq 45.

All eligible subjects will be stratified based on above four strata, to ensure a balance of gender and gingivitis across all study product groups and then randomized to a study product.

A subgroup analysis to evaluate and compare mean MGI and NBS in low (< 45) and high (\geq 45) bleeding sites groups will be conducted at 3 days (Visit 3), Week 1 (Visit 4), Week 2 (Visit 5) and Week 6 (Visit 6).

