To evaluate the efficacy of an experimental dentifrice containing 67% w/w sodium bicarbonate, 0.2% w/w HMW sodium hyaluronate and 0.221% w/w sodium fluoride compared to a 67% w/w sodium bicarbonate/ 0.221% w/w sodium fluoride dentifrice, with both compared to a fluoride control dentifrice, for the assessment of gingivitis, as measured by Modified Gingival Index (MGI), over 6 weeks twice daily use.	Mean MGI at 3 days, 1, 2 and 6 weeks.
To evaluate the efficacy of an experimental dentifrice containing 67% w/w sodium bicarbonate, 0.2% w/w HMW sodium hyaluronate and 0.221% w/w sodium fluoride compared to a 67% w/w sodium bicarbonate/ 0.221% w/w sodium fluoride dentifrice, with both compared to a fluoride control dentifrice, for the assessment of plaque accumulation, as measured by a Plaque Index (TPI; overall and interproximal), over 6 weeks twice daily use.	Mean TPI (overall and interproximal) at 3 days, 1, 2 and 6 weeks.
To evaluate and compare MGI and mean BI in low (<45 bleeding sites) and high (\geq 45 bleeding sites) BI subgroups following twice daily use of an experimental dentifrice containing 67% w/w sodium bicarbonate, 0.2% w/w HMW sodium hyaluronate and 0.221% w/w sodium fluoride, a 67% w/w sodium bicarbonate/ 0.221% w/w sodium fluoride dentifrice and a fluoride control dentifrice, over 6 weeks twice daily use.	Mean MGI and mean BI at 3 days, 1, 2 and 6 weeks within each subgroup (low and high number of bleeding sites)
Safety	
To assess the oral tolerability of an experimental dentifrice containing 67% w/w sodium bicarbonate, 0.2% w/w HMW sodium hyaluronate and 0.221% w/w sodium fluoride, a	Treatment-emergent adverse events over 6 weeks.

67% w/w sodium bicarbonate/ 0.221% w/w sodium fluoride dentifrice, and a fluoride control dentifrice over 6 weeks twice daily use.	
--	--

This PoP study will be considered successful if the experimental dentifrice containing 67% w/w sodium bicarbonate, 0.2% w/w HMW sodium hyaluronate and 0.221% w/w sodium fluoride demonstrates a reduction in the number of bleeding sites compared to a fluoride control dentifrice.

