The assumption of residual normality and variance homogeneity in ANCOVA analysis will be investigated through residual plots. If violated, data transformation or a nonparametric method (such as van Elteren test adjusting for gender and baseline number of bleeding sites stratification) will be used.

Mean Plaque index (TPI) (overall and interproximal) at 3 days, 1, 2 and 6 weeks

Mean overall plaque will be calculated taking the average over all tooth sites for a subject.

The interproximal plaque score will be calculated in the same way as for the overall scores but just based on the mesiofacial, distofacial, mesiolingual and distolingual surfaces.

Summary statistics including mean, SD, SE, median, minimum, maximum will be provided by visit and randomized treatment group for overall plaque and interproximal plaque. Raw means and SE will also be plotted over time by treatment group.

Overall plaque score and interproximal plaque score will be analyzed using ANCOVA model with treatment group, gender and number of bleeding sites strata as factors and baseline plaque score as covariate.

Adjusted means for all treatments and all pairwise treatment differences will be provided along with 95% confidence intervals.

The assumption of residual normality and variance homogeneity in ANCOVA analysis will be investigated through residual plots. If violated, data transformation or a nonparametric method (such as van Elteren test adjusting for gender and baseline number of bleeding sites stratification) will be used.

Subgroups analyses – Mean MGI and Mean BI at 3 days, 1, 2 and 6 weeks

A subgroup analysis to evaluate and compare mean MGI and number of bleeding sites in low (<45) and high (≥ 45) bleeding sites groups will be conducted using the same methodology as described above for each respective endpoint.

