- Experimental Dentifrice *vs* Positive Control Dentifrice
- Experimental Dentifrice *vs* Negative Control Dentifrice
- Positive Control Dentifrice *vs* Negative Control Dentifrice

Supra-gingival plaque will be assessed on the facial and lingual surfaces of the teeth using the Turesky Plaque Index (TPI). Each tooth surface will be divided into three areas; three scores will be recorded facially (mesiofacial, facial, distofacial) and three scores lingually (mesiolingual, lingual and distolingual) generating six scores per tooth. The plaque will be disclosed and scored for each site as follows:

Table 4-4 Turesky Plaque Index

Score	Description
0	No plaque
1	Separate flecks of plaque at the cervical margin
2	Thin continuous band of plaque (up to 1 mm) at the cervical margin
3	Band of plaque wider than 1 mm but covering < 1/3 of the tooth surface
4	Plaque covering \geq 1/3 but < 2/3 of the tooth surface
5	Plaque covering \geq 2/3 of the tooth surface

The mean Overall TPI score for each subject will be derived from the Total TPI score over all tooth sites divided by the number of tooth sites scored.

The mean Interproximal TPI score for each subject will be derived in the same way as for the overall scores but based on the mesiofacial, distofacial, mesiolingual and distolingual surfaces only.

The mean Overall TPI and mean Interproximal TPI scores will be analyzed using ANCOVA model with study product group, gender and number of bleeding sites strata as factors and baseline plaque score as covariate. Separately for Overall TPI score and Interproximal TPI score, adjusted means and their SEs for each study product group will be displayed with the study product group difference, SE, 95% CI of the difference, between-product p-value and percent difference between study product groups for mITT population.

4.4.3.5 Mean MGI and Mean BI at 3 days, 1, 2 and 6 Weeks within each subgroup (low and high number of bleeding sites)

Mean MGI and Mean BI at each visits will be analysed for the low and high NBS subgroup (Low NBS < 45, High NBS \geq 45) for the following product comparisons:

- Experimental Dentifrice *vs* Positive Control Dentifrice
- Experimental Dentifrice *vs* Negative Control Dentifrice
- Positive Control Dentifrice *vs* Negative Control Dentifrice

Experimental Dentifrice: 67% w/w sodium bicarbonate, 0.2% w/w high molecular weight sodium hyaluronate and 0.221% w/w sodium fluoride

208175

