Final Version 1.0 Statistical Reporting and Analysis Plan Text (Amendment 1),
10 Jun 2021

Mean MG1 score will be analyzed using ANCOVA model with treatment group, gender and number of bleeding sites strata as factors, baseline MG1 score as covariate and NBS strata (Low and High NBS) into study product groups as interaction effect. Adjusted means for all treatments and all pairwise treatment differences will be provided along with 95% confidence intervals.

Mean BI will be analyzed using ANCOVA model with treatment group and gender and number of bleeding sites strata as factors, baseline BI score as covariate and NBS strata (Low and High NBS) into study product groups as interaction effect. Adjusted means for all treatments and all pairwise treatment differences will be provided along with 95% confidence intervals.

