4.5.1.4 Mean MGI at 3 Days, 1, 2 and 6 Week

Descriptive statistics (n, mean, SD, SE, median, minimum, maximum) of the mean MGI score will be provided by visit and randomized study product group for the mITT population (CCI [REDACTED]). The mean MGI score will be analyzed using ANCOVA model in CCI [REDACTED] for mITT population.

The raw mean and SE of the MGI score will be presented graphically over time by study product group for the mITT population in CCI [REDACTED].

The MGI obtained for each tooth, surface and site will be listed by subject and visit in CCI [REDACTED] for all randomized subjects. The mean whole mouth MGI score will be listed by subject and visit in CCI [REDACTED] for all randomized subjects.

4.5.1.5 Mean TPI (Overall and Interproximal) at Day 3, 1, 2 and 6 Weeks

Descriptive statistics (n, mean, SD, SE, median, minimum, maximum) of the mean Overall TPI score (CCI [REDACTED]) and mean Interproximal TPI score (CCI [REDACTED]) will be provided by visit and study product group for the mITT population.

Results from ANCOVA analyses will be presented in CCI [REDACTED] (mean Overall TPI score) and in CCI [REDACTED] (mean Interproximal TPI score) for the mITT population.

Experimental Dentifrice: 67% w/w sodium bicarbonate, 0.2% w/w high molecular weight sodium hyaluronate and 0.221% w/w sodium fluoride

208175

Final Version 1.0 Statistical Reporting and Analysis Plan Text (Amendment 1),
10 Jun 2021

The raw mean and SE of the Overall TPI score for each study product group will be presented graphically over time for the mITT population in CCI [REDACTED].

The TPI obtained for each tooth, surface and site will be listed by subject and visit in CCI [REDACTED] for all randomized subjects. The mean Overall TPI score and mean Interproximal TPI score will be listed by subject and visit in CCI [REDACTED] for all randomized subjects.

4.5.1.6 Mean MGI and Mean BI at 3 days, 1, 2 and 6 weeks within each subgroup (low and high number of bleeding sites)

Mean MGI and Mean BI will be analysed in the same way as described in [Section 4.4.3.5](#) or the subgroup of low and high number of bleeding sites (Low NBS < 45, High NBS \geq 45) and summary will be presented in CCI [REDACTED] and CCI [REDACTED], respectively for the subgroup of low and high NBS for mITT population.

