4.7 Analysis of Other Variables

Repeat MGI and TPI assessments will be performed by the clinical examiner at Baseline (Visit 2), Day 3 (Visit 3), Week 1 (Visit 4), Week 2 (Visit 5) and Week 6 (Visit 6). At least 2 repeat assessments should be performed for each index on each clinical assessment day (≥ 1 in the morning; ≥ 1 in the afternoon). ‘Repeat’ subjects will be selected at random from those in attendance. Different subjects can be used for repeat MGI and TPI assessments.

The repeat dental assessments (MGI and TPI) will be compared to the original assessments and will be used to investigate intra-examiner variability. The repeat assessments will not be used in any efficacy analyses.

A weighted Kappa coefficient (κ), along with the 95% CI will be calculated to assess the intra-examiner reliability. Fleiss-Cohen weighted kappa will be calculated for the repeatability analysis. Reliability will be deemed:

- Excellent if $\kappa > 0.75$
- Fair to good if $0.4 \leq \kappa \leq 0.75$
- Poor if $\kappa < 0.4$

The first and repeat assessments for each tooth site will be cross tabulated for MGI (CCI [REDACTED]) and for TPI (CCI [REDACTED]). This analysis will be conducted for MGI using the MGI Repeatability population and for TPI using the TPI Repeatability population.

5 Changes to the Protocol Defined Statistical Analysis Plan

All changes from the originally planned statistical analysis specified in the protocol are outlined in [Table 5-1](#).

Table 5-1 Changes to Protocol Defined Analysis Plan

Protocol	Reporting & Analysis Plan	
Statistical Analysis section	Statistical Analysis Plan	Rationale for Changes
12.2.8 Exploratory Analyses Mean BI will be analyzed using ANCOVA model with treatment group and gender and number of bleeding sites strata as factors, and baseline BI score as covariate. Adjusted means for all treatments and all pairwise treatment differences will be	4.4.3.5 Mean MGI and Mean BI at 3 days, 1, 2 and 6 Weeks within each subgroup (low and high number of bleeding sites) Mean MGI score will be analyzed using ANCOVA model with treatment group, gender and number of bleeding sites strata as	ANCOVA model has been updated to incorporate interaction effect between high and low NBS and study product groups.

Experimental Dentifrice: 67% w/w sodium bicarbonate, 0.2% w/w high molecular weight sodium hyaluronate and 0.221% w/w sodium fluoride

208175

Final Version 1.0 Statistical Reporting and Analysis Plan Text (Amendment 1),
10 Jun 2021

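### Does naming two different bleeding outcomes for the exploratory low/high subgroup analysis leave that analysis undefined?

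*SAP*

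**What the plan says.** The last exploratory objective compares products within the low (<45) and high (≥45) baseline bleeding strata. Protocol Table 3-1 opens it with "To evaluate and compare MGI and mean BI in low" and high subgroups, and SAP 1.2 gives the endpoint as "Mean MGI and mean BI at 3 days, 1, 2 and 6 weeks within each subgroup".

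In Protocol 12.2.8 the heading of the subgroup paragraph also names mean MGI and mean BI. The one sentence beneath it reads differently: "A subgroup analysis to evaluate and compare mean MGI and number of bleeding sites in low" and high groups, to be analysed by the methods already set out for each endpoint. SAP 3.2 repeats that sentence almost word for word: "A subgroup analysis to evaluate and compare mean MGI and NBS in low" and high groups.

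The SAP sections that specify the analysis side with mean BI:

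- SAP 4.4.3.5 states "Mean MGI and Mean BI at each visits will be analysed for the low and high NBS subgroup". It then writes one ANCOVA for each of those two outcomes, with "NBS strata (Low and High NBS) into study product groups as interaction effect".
- SAP 4.5.1.6, which assigns the tables and figures, says "Mean MGI and Mean BI will be analysed in the same way as described in" SAP 4.4.3.5.
- Table 5-1 in SAP section 5 reproduces the protocol's NBS sentence in the protocol column and puts the mean MGI and mean BI models in the SAP column. Its stated reason is "ANCOVA model has been updated to incorporate interaction effect between high and low NBS and study product groups".

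**The concern.** SAP 3.2 is current text and says the NBS subgroup analysis will be done, yet no later SAP section says how. Table 5-1 is meant to record every departure from the protocol's analysis. It explains the added interaction but does not say that NBS was dropped. Read strictly, either an analysis is owed without a model or a change went unrecorded.

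The two outcomes are also different measures. NBS counts a site scored 1 and a site scored 2 alike (SAP 4.4.1.1). Mean BI weights a 2 above a 1 and divides by the number of sites scored (SAP 4.4.3.2). If both were open at unblinding, someone could report whichever looked better. NBS is the primary variable, so a subgroup finding on it would attract attention.

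**Working it through.** The documents give no figure to reproduce here, so the main check is to compare the passages.

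| Place | Bleeding outcome of the subgroup analysis |
|---|---|
| Protocol 1, objectives and endpoints table | mean BI |
| Protocol 3, Table 3-1 | mean BI |
| Protocol 12.2.8, heading of the subgroup paragraph | mean BI |
| Protocol 12.2.8, sentence under that heading | NBS |
| SAP 1.2, objectives table | mean BI |
| SAP 3.2 | NBS |
| SAP 4.4.3.5, comparisons and models | mean BI |
| SAP 4.5.1.6, tables and figures | mean BI |
| SAP Table 5-1, SAP column | mean BI |

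That is seven places for mean BI and two for NBS. (The protocol column of Table 5-1 only reproduces the Protocol 12.2.8 sentence.) The two NBS places share their wording, so they amount to one sentence carried forward rather than two separate commitments. No endpoint table lists an NBS subgroup result.

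**Is a model missing?** The SAP has one subgroup model for mean MGI, one for mean BI and none for NBS. It does have an NBS model: SAP 4.4.1.2 for week 6, extended to the earlier visits by SAP 4.4.3.1 and 4.5.1.2. The Protocol 12.2.8 sentence refers back to each endpoint's own method. For NBS that means the primary ANCOVA (product, gender, baseline NBS) run within each stratum. What is absent is only a subgroup-specific NBS model in the SAP.

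**How different are the scales?** Protocol 4.2 gives 120 to 168 sites per subject. Take NBS = 40 as an illustration, with every bleeding site scored 1 or every one scored 2:

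- 168 sites: 40/168 = 0.24 to 80/168 = 0.48
- 120 sites: 40/120 = 0.33 to 80/120 = 0.67

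So the measures are not interchangeable for a single subject. This does not show that product contrasts would differ, since both come from the same site scores.

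**What would adding NBS cost?** Each outcome has 2 strata × 4 visits × 3 comparisons = 24 contrasts. Mean MGI and mean BI give 48, and NBS would make 72. For precision, take 36 evaluable per group (Protocol 12.1), hence 108 in all. The interaction model has 8 parameters, so there are 100 residual df and t = 1.984. The documents do not give the stratum split. Assuming 30% to 70% of each group falls in a stratum (11 to 25 subjects), the 95% half-width of a within-stratum contrast is:

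- 11 per group: 1.984 × √(2/11) = 0.85 residual SD
- 25 per group: 1.984 × √(2/25) = 0.56 residual SD

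In SD units these are the same for any outcome. They show how little an extra set of contrasts would add. They do not measure the inconsistency itself.

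**The case for a change.** The strongest case for acting is that a repair costs a few lines and closes a choice that should be closed before unblinding. SAP 3.2 is operative, Table 5-1 is silent on the outcome, and a programmer asked for NBS would face two defensible models: separate fits within strata, as the protocol implies, or an interaction model like those in SAP 4.4.3.5.

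Some of this stands. The wording does conflict, and the rationale in Table 5-1 is incomplete. The risk of selective reporting is small, though. The endpoint tables and the SAP section assigning the displays both fix mean BI, so an NBS subgroup result put forward in its place would be visibly off the stated endpoint.

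A related request is to state that the product-by-stratum interaction will be reported. SAP 4.4.3.5 lists adjusted means and pairwise differences as output and does not mention the interaction estimate. The list of data displays in Attachment 1 is redacted, so its absence from the planned output cannot be inferred. The fitted model yields the estimate in any case, and the point does not bear on which outcome is analysed.

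**Conclusion.** No change is called for. The inconsistency is a clerical carry-over: SAP 3.2 repeats a protocol sentence that disagrees with its own heading and with the endpoint tables. The sections that specify and display the analysis give usable models for mean MGI and mean BI, so aligning SAP 3.2 with them would change no estimate and no conclusion. Adding NBS as a third outcome is a matter of preference, with 24 further imprecise contrasts as its price.

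The effect is confined to one exploratory analysis. The primary and secondary comparisons of NBS at week 6, their model and their significance level do not depend on it. Leaving the bleeding stratum out of the primary ANCOVA is deliberate and explained in SAP 4.4.1.2. This conclusion assumes that analysts follow the endpoint tables and SAP 4.4.3.5 and 4.5.1.6. The redacted display list, which might name an NBS subgroup table, could not be checked. If it does name one, Protocol 12.2.8 supplies the method.
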